The metastases are randomized by block randomization and are done separately in each patient. The randomization is performed by an extern unit, using the computer program nQuery Adviser 7.0. The bleomycin and calcium are mixed and labeled by an extern unit, and since both calcium and bleomycin are transparent and identical in volume, it is possible to label the syringes in a manner to blind the treating doctor. The syringes are labeled with numbers according to the metastases so syringe number '1' goes to metastasis number '1' and so on. The randomization code is kept behind locked doors, and is not accessible to the treating doctor. The randomization code is revealed for each patient after follow up, 6 months after treatment.

The randomization code can be revealed before completion of the investigation, if the investigator believes that the treatment causes so serious unexpected events or reactions, that a continuation of treatment is unacceptable.

As the randomization is done separately in each patient, it is possible to break the code for the individual patient, without breaking the code of the other participants.

Dose

The dose of calcium chloride was amended to 220 mmol/L from 168 mmol/L in this trial.

Volume of calcium chloride is dependent on tumor volume. Smaller tumors should have bigger volume per cm^3 , as smaller tumors are expected to have a bigger loss of injected medicine into the surrounding tissue. The dose volume is calculated according to the 'European Standard Operating Procedure of the Electrochemotherapi (ESOPE)':

Calcium

Calcium chloride 220 mmol/L (9 mg/ml):

- Tumor $< 0,5 \text{ cm}^3$ – 1 ml / cm^3 tumor volume
- Tumor $> 0,5 \text{ cm}^3$ – 0,5 ml/ cm^3 tumor volume

Tumor volume = $ab^2\pi/6$ (a=longest diameter, b= longest diameter perpendicular to a)

Bleomycin

Both dose and volume of bleomycin is standard according to ESOPE

Bleomycin 1000 IU/ml:

- Tumor $< 0,5 \text{ cm}^3$ – 1 ml / cm^3 tumor volume
- Tumor $> 0,5 \text{ cm}^3$ – 0,5 ml/ cm^3 tumor volume

Tumor volume = $ab^2\pi/6$ (a=longest diameter, b= longest diameter perpendicular to a)

Maximum of injected bleomycin per tumor will be 1500 IU and total dose per treatment 7500 IU. Normal maximum limit for bleomycin is 15.000 IU/ m^2 body surface area.

Bleomycin and calcium chloride are mixed and labeled according to current guidelines. The mixtures will be used in a maximum of 6 hours after mixing.

The Electrical Pulses

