This is a randomized non-inferiority study comparing calcium electroporation with electrochemotherapy with intratumoral injection of bleomycin. For dimensioning tumor number, analysis of non-inferiority study is used. Tumor response is evaluated at each follow up with surveying. Documentation is done with digital color photography, including a ruler to estimate tumor size. Primary evaluation of the response will be based on criteria similar RECIST guidelines 1.1. Tumor response was analyzed using Fisher's exact test on objective response 6 months after treatment.

Response rate of tumors ≤ 3 cm treated with ECT with bleomycin is 85-100% (existing data). In this study, we have chosen not to put the expected response rate for ECT too high, but estimate it to 85%. We have no clinical results for the treatment of calcium electroporation, but on the basis of preclinical studies, the response rate for calcium electroporation is estimated to 70%. In order to detect a clinical difference in the two treatments of 15%, with a significant level of 0.1, and a power

of 80%, a minimum of 34 evaluable tumors need to be included. (Sample Size Calculator: https://www2.ccrb.cuhk.edu.hk/stat/proportion/tspp_sup.htm)

The metastases are evaluable 4 weeks after treatment. If a patient is excluded from the protocol before 4 weeks follow up, the patient will be replaced.

The number of patients that are being pulled out of the trial will be listed and primary reason for the exclusion will be described.

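### Fisher's exact test at the stated 0.1 level is conservative with about 34 tumours; Boschloo's test would recover a modest amount of power within the same level

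*Combined protocol and SAP*

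**What the plan says.** All but one of the elements stand in the Statistical analysis section of the combined protocol and SAP.

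- Test: Fisher's "exact test on objective response 6 months after treatment". No mid-P or unconditional version is mentioned.
- Level, power and size: "with a significant level of 0.1, and a power" "of 80%, a minimum of 34 evaluable tumors need to be included". Sidedness and the number per arm are not given.
- Assumed rates: for bleomycin, "we have chosen not to put the expected response rate for ECT too high, but estimate it to 85" per cent; for calcium, "the response rate for calcium electroporation is estimated to 70" per cent.
- Frame: "This is a randomized non-inferiority study comparing calcium electroporation with electrochemotherapy", although the sizing sentence begins "In order to detect a clinical difference in the two treatments of 15" per cent.
- Allocation (Randomization section): "The metastases are randomized by block randomization and are done separately in each patient". With one to six randomized metastases per patient, an exactly equal split is not guaranteed.

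**The concern.** Fisher's test conditions on the total number of responders. With few tumours and high response rates, only a few outcomes are possible given that total, so the p-value moves in large steps. The real chance of a false positive then falls below the nominal level. A trial that states a 0.1 level, and so accepts a fairly high error rate, does not get the power that this level could buy.

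What is at stake is efficiency, not validity. In a trial asking whether calcium can replace bleomycin, lower power makes a real deficit with calcium easier to miss, and a non-significant result easier to misread as similarity.

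**Working it through.** **Inputs.** From the Statistical analysis section: level 0.1, rates 85% (bleomycin) and 70% (calcium), 34 tumours. Assumptions, because the plan is silent: 34 is the total, tumours are independent, the split is equal or nearly so, and sidedness is either one or two.

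**The plan's own figure.** The one calculation found that returns 34 from the stated inputs uses a one-sided level of 0.1 and a distance of 0.30, that is, the 15-point difference plus a 15-point margin:

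n per arm = (0.85×0.15 + 0.70×0.30) × (1.2816 + 0.8416)² / 0.30² = 0.3375 × 4.508 / 0.09 = 16.9, so 17 per arm and 34 in total.

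This supports reading 34 as a total. It suggests a one-sided level but does not establish one.

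**Method.** Let P_F(x, y) be Fisher's p-value for x and y responders out of n₁ and n₂.

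- True size at a common rate p: the sum of b(x; n₁, p) × b(y; n₂, p) over all tables with P_F ≤ 0.1, where b is the binomial probability. The maximum is taken over p from 0.001 to 0.999.
- Boschloo's p-value: the maximum over p of Pr{P_F(X, Y) ≤ P_F(x, y)}. It uses Fisher's p-value as its statistic and is never larger than it, so it rejects whenever Fisher's test does.
- Power: the same sum with rates 0.85 and 0.70.

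All tables were enumerated. Splits are bleomycin:calcium and entries are percentages.

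Two-sided, level 0.1:

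| Split | Fisher max size | Fisher size at 85% | Boschloo max size | Boschloo size at 85% | Fisher power | Boschloo power |
|---|---|---|---|---|---|---|
| 17:17 | 5.8 | 2.6 | 9.0 | 4.8 | 15.5 | 21.9 |
| 16:18 | 7.2 | 5.7 | 9.8 | 7.7 | 20.5 | 25.7 |
| 18:16 | 7.2 | 5.7 | 9.8 | 7.7 | 21.1 | 27.9 |
| 15:19 | 7.6 | 4.6 | 9.8 | 7.7 | 17.4 | 26.1 |
| 19:15 | 7.6 | 4.6 | 9.8 | 7.7 | 18.9 | 26.3 |
| 17:18 | 9.0 | 4.9 | 9.0 | 8.0 | 18.8 | 23.7 |
| 18:17 | 9.0 | 4.9 | 9.0 | 8.0 | 23.8 | 29.2 |

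The gain in power is about 5 to 9 points.

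One-sided (bleomycin better), level 0.1:

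| Split | Fisher max size | Boschloo max size | Fisher power | Boschloo power |
|---|---|---|---|---|
| 17:17 | 6.1 | 9.7 | 25.8 | 35.3 |
| 16:18 | 6.5 | 9.8 | 25.4 | 38.0 |
| 18:16 | 6.5 | 9.8 | 28.5 | 37.4 |
| 15:19 | 5.8 | 9.8 | 26.9 | 38.1 |
| 19:15 | 5.8 | 9.8 | 22.4 | 36.0 |
| 17:18 | 5.1 | 9.2 | 25.2 | 38.6 |
| 18:17 | 5.1 | 9.2 | 28.3 | 36.3 |

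The gain is about 8 to 14 points.

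**An example.** At 17:17 two-sided, 15 versus 10 responders gives a Fisher p of 0.118, which is not significant at 0.1. Boschloo's test rejects every table with a Fisher p up to 0.157, including this one, and its error rate never exceeds 9.0%.

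**How much is recovered.** At 17:17 two-sided with both rates at 85%, Fisher's test leaves 10 − 2.6 = 7.4 points of the level unused. Boschloo's test recovers 4.8 − 2.6 = 2.2 of them.

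**If 34 meant per arm.** Two-sided, Fisher's maximum is 6.8% and Boschloo's 9.7%; power goes from 32.7% to 39.6%.

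**Other substitutes.** At 17:17 two-sided, the uncorrected chi-square test reaches a 12.2% error rate. Mid-P Fisher stays at 9.4% two-sided but reaches 11.5% one-sided. Neither guarantees the level.

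**The case against.** Fisher's test is valid and conventional for small tables, and whether to condition on the margins is partly a matter of taste. Nothing false is made more likely by keeping it. That stands, and it is why the point is minor.

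Four stronger readings are tempting, and the documents do not support them.

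- A reader might infer that about half or more of the 0.1 level is always lost. At 85% with a two-sided 17:17 comparison about three quarters is unused, but the plan fixes neither the split nor the sidedness. At 16:18 the unused share is 28% to 43%. At 17:18 Fisher's maximum of 9.0% matches Boschloo's.
- A reader might infer that the loss is wholly avoidable. Much of it is discreteness that Boschloo's test does not recover either.
- A reader might infer that power is halved. At 17:17 two-sided the relative loss against Boschloo's test is (21.9 − 15.5)/21.9 = 29%.
- A reader might infer that a sharper test repairs the trial. Boschloo's power stays below 40% in every near-34 split above, against a stated 80%; that shortfall comes from the sample size. Both tests also address the hypothesis of no difference, while the section calls the study non-inferiority. If the analysis is recast with a margin, these magnitudes no longer describe it.

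Timing is a fair objection too. The Trial Design and Randomization sections open the code patient by patient at 6 months, and the analysis sentence is in the past tense. Moving to a more powerful test after results by arm are visible carries its own risk.

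**Conclusion.** The concern holds as a minor efficiency point. With about 34 independent tumours, Fisher's test at 0.1 has a true maximum error rate of 5.8% to 9.0% two-sided, depending on the split, and about 5% to 6.5% one-sided. Boschloo's test kept its error rate at or below 10% in every split checked. For 85% versus 70% it gained about 5 to 9 points of power two-sided and 8 to 14 one-sided.

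The figures rest on 34 being the total, near-equal arms and independent tumours. The last is doubtful, since a patient can contribute up to six tumours to the response analysis. The direction of the finding does not depend on the split or sidedness, but the exact digits do.

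**What to change.** If a test of difference is kept, name Boschloo's exact unconditional test at the 0.1 level in place of Fisher's, and say whether it is one-sided or two-sided. This costs one sentence, needs no new data, and uses standard software.

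If the primary analysis is recast as non-inferiority with a margin, use an unconditional exact or score-type confidence bound on the difference in response rates instead. If the comparison is stratified by patient, a mid-P exact stratified test is an option, with a note that it does not guarantee the level.

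Fix the choice before any analysis by arm. If codes are already open, keep Fisher's test as primary and report Boschloo's as a sensitivity analysis. The sample size and the non-inferiority hypothesis need their own corrections.

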Calcium Electroporation for Treatment of Cutaneous Metastases; randomized double blind phase II study

NCT03628417

Primary Completion Date: 04/06/2019

Last update: 03/10/2019

Last release: 09/24/2019

Introduction

Background

Electroporation is a method that can facilitate transport of molecules across the cell membrane and into the cell by means of electrical pulses. The method can be used with molecules that normally have difficulty passing the cell membrane such as chemotherapy (electrochemotherapy). Electrochemotherapy (ECT) is used in cancer therapy, where chemotherapy is administered intratumoral or intravenous, then followed by electrical pulses applied directly on the tumor. The chemotherapy accumulates in the cancer cells which results in an increased cytotoxic effect. The most used chemotherapeutic drug used in electrochemotherapy is bleomycin. Electrochemotherapy is a well-documented local treatment form for especially cutaneous tumors. Today, the treatment is used mostly in palliative care in more than 140 centres around Europe.

In vitro and *in vivo* studies have shown that the combination of calcium and electroporation is an effective method in killing cancer cells without serious side effects. This new combination opens the possibility of replacing bleomycin with calcium in treatments with electroporation.

Calcium electroporation is a local treatment where calcium is administered intratumoral and followed by electrical pulses applied on the tumor.

Calcium electroporation would be possible to use on patients for whom chemotherapy is contradicted e.g. severe lung functions impairment, pregnant woman etc. Calcium electroporation is a simple and inexpensive cancer treatment that does not involve any administration of cytotoxic chemotherapy, and can be performed by surgeons, radiologists as well as oncologists. Both electroporation equipment and calcium are already being used in the clinic, so the treatment can easily be implemented.

Method

We wish to examine calcium electroporation on patients with cutaneous metastases from any histology and compare the effect with electrochemotherapy. On evaluations on tumor response we want to investigate if calcium can replace bleomycin in the treatment of cutaneous metastases.

To investigate that we use a randomized double blinded phase II study on patients with small cutaneous metastases. The metastases will be randomized into two treatment arms:

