1. Intratumoral injection with calcium, followed by electrical pulses.
2. Intratumoral injection with bleomycin, followed by electrical pulses.

Randomization will be done separately on each metastasis

Objectives

Primary Objective

The primary objective is to evaluate and compare response rate of calcium electroporation and electrochemotherapy on cutaneous metastases. Response will be evaluated individual on each treated metastasis by clinical examination and documented by clinical photo before and after treatment. Evaluation is performed according to RECIST-like guidelines.

Secondary Objective

The secondary objective is to register adverse events for calcium electroporation and electrochemotherapy respectively. Adverse Events (AE) and Serious Adverse Events (SAE) will be evaluated and graded according to Common Terminology Criteria for Adverse Events (CTCAE) version 4.0.

Tertiary Objective

The tertiary objective is to register if calcium affects the current strength in electroporation treatments. Maximum given current in metastases treated with calcium will be compared to maximum given current in metastases treated with bleomycin.

Trial Design

Trial Design for Treatment of Cutaneous Metastases

It is a randomized double blinded phase II study (adapted from Denmark) comparing the effect of calcium electroporation with ECT with bleomycin on patients with cutaneous metastases of any histology. As calcium and bleomycin are administered intratumoral, only small metastases from 0.5-3cm will be treated. The treatments will be compared in tumor response and adverse events. Treatment will be done in a palliative purpose.

Cancer patients with cutaneous involvement have often several metastases. A maximum of ten metastases will be included per patient. One to six metastases (depending on the patient's number of metastases) will be numbered 1-6 and randomized into one of two treatment arms:

1. Intratumoral calcium followed by electroporation
2. Intratumoral bleomycin followed by electroporation

Randomization will be performed separately on each metastasis, so the patient may receive both treatments. Calcium and bleomycin will be mixed into syringes labeled with numbers according to the metastases and both treating doctor and patient will be blinded to the content of the syringes.

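### At the plan's own response rates (bleomycin 85%, calcium 70%), 34 evaluable tumours give Fisher's test about 16% (two-sided) or 26% (one-sided) power at level 0.1, not the stated 80%.

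*Combined protocol and SAP*

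**What the plan says.** The Statistical analysis section calls the trial a non-inferiority study and says of the sample size: "For dimensioning tumor number, analysis of non-inferiority study is used". For bleomycin electrochemotherapy, "we have chosen not to put the expected response rate for ECT too high, but estimate it to 85" per cent. On preclinical grounds, "the response rate for calcium electroporation is estimated to 70" per cent. The target is then put as a difference to be found: "In order to detect a clinical difference in the two treatments of 15%, with a significant level of 0.1" and 80% power, for which "a minimum of 34 evaluable tumors need to be included". The only further support is a link to an online calculator. The analysis is Fisher's "exact test on objective response 6 months after treatment".

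The section names no non-inferiority margin. It does not say whether 0.1 is one-sided or two-sided, or whether 34 is a total or a number per arm. No allocation ratio is given. Under Trial Design, up to six metastases per patient "will be numbered 1-6 and randomized into one of two treatment arms", and the sample size makes no allowance for several tumours coming from one patient.

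**The concern.** A 15-point difference between 85% and 70% is modest, and 34 is very few tumours for it. The paragraph also mixes two aims. Detecting a difference and showing non-inferiority are separate calculations, and the expected deficit of 15 points is the only figure available to serve as a margin.

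The power claim governs how a null result will be read. The Method section says "we want to investigate if calcium can replace bleomycin in the treatment of cutaneous metastases". A reader who believes the trial had 80% power to find a 15-point deficit will take a non-significant Fisher test as evidence that calcium can be used instead. If the real power is far lower, that inference fails, and it fails in favour of the new treatment.

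**Working it through.** **Inputs from the Statistical analysis section.** Bleomycin 0.85, calcium 0.70, difference 0.15, level 0.1, power 80%, 34 tumours, Fisher's exact test.

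**Assumptions.** Equal allocation (17 + 17), independent tumours, both sidednesses tried. Where a margin is needed, 15 points is assumed.

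**Constants.** z(0.90) = 1.2816, z(0.95) = 1.6449, z(0.80) = 0.8416. The squared sums are (1.2816 + 0.8416)² = 4.508 (one-sided 0.1) and (1.6449 + 0.8416)² = 6.183 (two-sided 0.1). The variance term is 0.85 × 0.15 + 0.70 × 0.30 = 0.3375.

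**1. Trying to reproduce 34 in the stated direction**

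| Calculation | One-sided 0.1 | Two-sided 0.1 |
|---|---|---|
| Difference, unpooled | 4.508 × 0.3375 / 0.0225 = 67.6, so 68 per arm (136) | 6.183 × 0.3375 / 0.0225 = 92.7, so 93 per arm (186) |
| Difference, pooled (mean rate 0.775) | 68.97, so 69 per arm (138) | 94.8, so 95 per arm (190) |
| Fisher, full enumeration, first size reaching 80% | 81 per arm (162), power 0.802 | 106 per arm (212), power 0.801 |

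Non-inferiority with the assumed margin, one-sided 0.1:
- Both rates 85%: 4.508 × (2 × 0.85 × 0.15) / 0.15² = 4.508 × 0.255 / 0.0225 = 51.1, so 52 per arm (104).
- Calcium 70%, bleomycin 85%: the denominator is (0.15 − 0.15)² = 0, so no finite size exists.

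None of these is 34, in total or per arm.

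**2. Where 34 does appear.** With the direction reversed (calcium 15 points better, margin 15 points, one-sided 0.1), the distance to the margin is 0.30. Then 4.508 × 0.3375 / 0.30² = 16.90, so 17 per arm and 34 in total. Whether this was the calculator entry cannot be checked from the documents.

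**3. Power that the design has.** Fisher's test at level 0.1, 85% against 70%, by full enumeration of two independent binomials:

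| Bleomycin / calcium tumours | Two-sided | One-sided |
|---|---|---|
| 17 / 17 | 0.155 | 0.258 |
| 14 / 20 | 0.175 | 0.221 |
| 20 / 14 | 0.218 | 0.290 |
| 34 / 34 | 0.327 | 0.474 |

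Non-inferiority, both rates 85%, assumed margin, one-sided 0.10:
- 17 per arm, normal approximation: Φ(0.15 / √(0.255/17) − 1.2816) = 0.477. Exact enumeration gives 0.526 with a Wald bound and 0.443 with a Newcombe score bound.
- 34 per arm: 0.674 (normal approximation) and 0.683 (exact Wald).

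If calcium is truly 70%, the chance of declaring non-inferiority with that margin is the type I error. With the Wald bound it is 0.119, 0.101, 0.103 and 0.101 at 17, 34, 52 and 200 per arm. It is not counted here as a shortfall of 34.

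**4. What a null result would mean.** Suppose 15/17 bleomycin and 11/17 calcium tumours respond. Fisher's p is 0.2245 two-sided and 0.1123 one-sided, so neither is significant at 0.1. The difference is −0.235 with standard error 0.1398. The one-sided 90% bound is −0.235 − 1.2816 × 0.1398 = −0.414, which still allows calcium to be 41 points worse.

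**5. Dependence between tumours.** The documents give no within-patient correlation, so the variance of the difference was scaled by an assumed factor. These are normal approximations at 17 per arm and should be compared with their own factor-1 column, not with the Fisher figures above.

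| Calculation | Factor 0.5 | Factor 1 | Factor 1.5 |
|---|---|---|---|
| Non-inferiority, both 85% | 0.674 | 0.477 | 0.389 |
| Difference, one-sided | 0.589 | 0.414 | 0.340 |
| Difference, two-sided | 0.445 | 0.281 | 0.219 |

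For 80% power the factor would have to fall to about 0.33, 0.25 and 0.18 respectively.

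**The case against.** The strongest reply is that tumours are randomised in blocks within each patient. If responses correlate strongly within patients, a paired analysis could have much smaller variance than two independent samples. This stands in part: dependence fails to restore 80% only within the assumed range of factors from 0.5 to 1.5, and a stronger reduction cannot be excluded without a correlation. But the plan claims no such gain, and the Fisher test it names ignores pairing.

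Fisher's test is also conservative, and the study is declared as non-inferiority. Yet Fisher is the plan's own choice, the normal formulas still require at least 136 tumours for the difference, and the non-inferiority reading needs 104 on a favourable assumption. The power under that reading depends on the method: the Wald figure of 53% comes with a type I error of 11.9%, while the Newcombe bound gives 44%. About 44% to 53% is the fair range.

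The 15-point margin is not the sponsor's, and the reversed direction is an inference from arithmetic. Both are correct cautions, and the Fisher result depends on neither. Finally, this is a small palliative phase II study with a 2019 primary completion date. A small study is acceptable, and the design can no longer change. What can still change is the stated power and the reading of the result.

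**Conclusion.** The concern holds. At the plan's own rates, 34 evaluable tumours do not give 80% power. Fisher's test at level 0.1 has about 16% (two-sided) or 26% (one-sided) with 17 per arm, and 33% or 47% if 34 is per arm. With calcium truly 15 points worse, the trial would miss that deficit about 84% (two-sided) or 74% (one-sided) of the time at 17 per arm. These figures assume independent tumours and equal allocation; the unequal splits shown give 18% to 22% two-sided and 22% to 29% one-sided. A non-significant Fisher test from this trial therefore cannot establish that calcium can replace bleomycin.

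**What to change.** Withdraw the 80% power statement in the Statistical analysis section. Suggested replacement:

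> With 34 evaluable tumours in total (about 17 per arm), Fisher's exact test at level 0.1 has about 16% (two-sided) or 26% (one-sided) power for response rates of 85% and 70%. These figures assume independent tumours and equal allocation, although up to six tumours come from one patient.

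The sponsor should state whether 0.1 is one-sided or two-sided and whether 34 is a total. If it is per arm, the figures become 33% and 47%. The sponsor should also state and justify a non-inferiority margin separately from the expected difference. If that margin is 15 points, add that power at one-sided 0.10 is about 44% to 53% when both true rates are 85% (67% to 68% at 34 per arm), and that the roughly 10% chance of success when calcium is truly 70% is type I error.

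Report the response-rate difference with its one-sided 90% bound. The expected distance from estimate to bound at 17 per arm is 1.2816 × √(0.255/17) = 0.157 to 1.2816 × √(0.3375/17) = 0.181, or 16 to 18 points; at 34 per arm it is 11 to 13. Do not present a non-significant Fisher test as evidence for replacement.

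The cost is one reworded paragraph and one reported interval. With primary completion in 2019 and the analysis already described in the past tense, no extra enrolment is asked for. The downside is a much less favourable stated power.

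### Does the gap between 4-week evaluability and the 6-month test leave the response denominator undefined?

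*Combined protocol and SAP*

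**What the plan says.** All the relevant rules are in the Statistical analysis section of the combined protocol and SAP. The sample size statement is that "a minimum of 34 evaluable tumors need to be included". Directly after the calculator reference comes "The metastases are evaluable 4 weeks after treatment", and then the replacement rule: "If a patient is excluded from the protocol before 4 weeks follow up, the patient will be replaced". The efficacy comparison is "Fisher's exact test on objective response 6 months after treatment". On withdrawals the plan says "The number of patients that are being pulled out of the trial will be listed and primary reason for the exclusion will be described".

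The unit of analysis is set elsewhere. Under Trial Design for Treatment of Cutaneous Metastases, one to six metastases per patient "will be numbered 1-6 and randomized into one of two treatment arms", and "Randomization will be performed separately on each metastasis, so the patient may receive both treatments". Metastases kept for biopsy are not assessed for response. The Randomization section says that allocation is blocked within each patient and that a patient's code is normally opened at the 6-month follow-up. Under Primary Objective, "The primary objective is to evaluate and compare response rate of calcium electroporation and electrochemotherapy on cutaneous metastases".

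**The concern.** Two time points are used and nothing joins them. A tumour can be evaluable at 4 weeks, fall outside the replacement rule, and then have no 6-month assessment. It could be left out, counted as a non-response, or given its last recorded response, since response is recorded at every follow-up. The plan does not choose. The promised list of withdrawals counts patients, while randomisation and response are by tumour, so that list alone does not give the 6-month denominator by arm.

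This could matter for three reasons. Treatment is palliative and follow-up runs about five months past the replacement window, so later losses are plausible. One patient can carry up to six tumours. And the primary objective is to evaluate each response rate as well as to compare them, so each arm's rate is itself a result. A reader could not interpret it without knowing whether it is a share of assessed tumours or of all evaluable tumours.

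**Working it through.** **Inputs from the Statistical analysis section.** Response rates 85% (bleomycin) and 70% (calcium); level 0.1; power 80%; 34 evaluable tumours. **Assumptions.** 34 is a total split 17 and 17 (the plan does not say total or per arm), Fisher's test is two-sided, and tumours are independent. No loss rate after 4 weeks is given.

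**The plan's figure.** The unpooled formula at one-sided 0.1 is n per arm = (1.282 + 0.842)² × (0.85×0.15 + 0.70×0.30) / 0.15² = 4.508 × 0.3375 / 0.0225 = 67.6, so 68 per arm. The stated 34 is therefore not reproduced. It appears as 2 × 17 only if the distance is 0.30 (4.508 × 0.3375 / 0.09 = 16.9), which is not the scenario in the text. That is a separate matter, and nothing below depends on how 34 was derived.

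**Which tumours are the 34?** The count of evaluable tumours is followed by a sentence placing evaluability at 4 weeks and by a replacement rule at the same visit. The ordinary reading is that 34 counts tumours evaluable at 4 weeks. What remains open is only the 6-month outcome of a tumour lost later.

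**Share carried by one patient.** 1/34 = 2.9% to 6/34 = 17.6%. If 34 is per arm, 1/68 = 1.5% to 6/68 = 8.8%.

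**Largest single-patient loss (six tumours, three per arm), bleomycin versus calcium.**

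| Rule | Bleomycin | Calcium | Difference |
|---|---|---|---|
| Assessed only | 12/14 = 85.7% | 10/14 = 71.4% | 14.3 points |
| Missing = non-response | 12/17 = 70.6% | 10/17 = 58.8% | 11.8 points |
| Missing = response | 15/17 = 88.2% | 13/17 = 76.5% | 11.8 points |

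The all-evaluable rate in each arm can lie anywhere in a band of 3/17 = 17.6 points. A last-observed-response rule falls inside that band. With a two-tumour patient (one per arm) the band is 1/17 = 5.9 points.

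**Effect on the test.** Responders among assessed tumours were enumerated as Binomial(m, 0.85) and Binomial(m, 0.70). For each outcome, Fisher's test at p ≤ 0.1 on m versus m was compared with the same responders over 17 versus 17.

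| Lost per arm | m | Significant, assessed only | Significant, missing = non-response | Verdicts differ |
|---|---|---|---|---|
| 1 | 16 | 14.1% | 10.6% | 3.5% |
| 3 | 14 | 13.5% | 5.7% | 7.7% |

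Every change is from significant to non-significant. At 34 per arm the corresponding disagreement is 3.0% (33 assessed) and 8.9% (31 assessed).

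**Expected difference under equal loss d unrelated to response.** Assessed-only keeps 15 points. Missing-as-non-response gives 15 × (1 − d): 13.5, 12 and 10.5 points at assumed d of 10%, 20% and 30%.

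**The case for a change.** The strongest case for acting is that each arm's rate is a primary result and the rule is unwritten. With three tumours lost per arm, switching from assessed-only to missing-as-non-response cuts the chance of a significant difference from 13.5% to 5.7%. In a study described as non-inferiority, a smaller difference would favour calcium. Loss that depends on arm and response could do more. Suppose 4-week response is 14/17 versus 12/17, and three bleomycin responders and three calcium non-responders are then lost. The difference is +11.8 points with last response carried forward (82.4% versus 70.6%) and −7.1 points among assessed tumours (11/14 = 78.6% versus 12/14 = 85.7%).

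Part of this stands. The rule is unwritten, a patient-level withdrawal list does not supply a tumour denominator, and one sentence in the report stating the rule would be good practice.

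The rest carries less weight. The sign reversal needs opposite kinds of tumour to be lost from the two arms. Patients, not single tumours, are excluded, allocation is blocked within patient, and the code is normally closed until 6 months, so a lost patient will usually take tumours from both arms for reasons unconnected with treatment. The exceptions are patients with one tumour or an uneven split, and the block size is not stated. The argument that shrinkage favours calcium holds only if a non-significant Fisher result is read as non-inferiority. Fisher's test here has no margin, and that is a different issue from the denominator.

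**Conclusion.** No change to the plan follows. The omission is a gap that analysts fill sensibly: a 6-month Fisher table is made of tumours with a 6-month response, and rates shown as n/N by arm beside the 4-week-evaluable count make the denominator visible. Choosing another rule is a trade-off. Assessed-only preserves the expected difference if loss is equal and unrelated to response, but can flatter the rates if unseen tumours did worse. Missing-as-non-response guards the rates but shrinks the difference. Last observed response keeps every tumour but assumes that the earlier status lasted. The documents give no ground for calling one of these right and the others wrong.

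The size is modest for the comparison and larger for the separate rates. For one lost patient with two to six tumours, each arm's rate has a 5.9 to 17.6 point band and the verdict changes in about 3.5% to 8% of trials. In the six-tumour example the difference between arms moves by 2.5 points (14.3 − 11.8) between the two denominators. These figures assume 17 tumours per arm, independent tumours, an even split of the lost patient's tumours and the planned 85% and 70%. They describe one lost patient, not a forecast. Several losses after 4 weeks, or losses concentrated in one arm, would widen them and would make a sensitivity row in the report worth having.
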